9.6.5 Beck Depression Inventory (BDI)-II

No statistical testing will be performed on BDI-II. The number and percentage of subjects in each of the 4 severity grade categories will be provided by treatment group.

9.6.6 Columbia Suicide Severity Rating Score (C-SSRS)

No statistical testing will be performed on C-SSRS. The number and percentage of subjects in each of the 5 categories describing suicidal behavior and ideation will be summarized by treatment group.

9.6.7 Physical Measurements

The analyses of weight will include summary statistics over time by treatment group. The number and percentage of subjects with at least one post-treatment weight measurement meeting the following criteria will be reported:

Decrease of 7% from baseline or increase of 7% from baseline

9.6.8 Electrocardiogram

The ECG measurements from this clinical study will be performed as per standard of care for routine safety monitoring, rather than for purposes of assessment of potential QTc effect. Since these evaluations may not necessarily be performed under the

rigorous conditions expected to lead to meaningful evaluation of QTc data, summaries and statistical analyses of ECG measurements are not planned, and these data would not be expected to be useful for meta-analysis with data from other studies.

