A comprehensive safety monitoring plan has also been included in this study in order to capture any possible risks. To assess potential impact on all body systems, all adverse events will be collected from the first dose through the end of study and various laboratory tests of blood (eg, red blood cells [RBC], white blood cells [WBC], liver function test, creatinine phosphokinase [CPK], cholesterol, potassium, HbA1C, glucose) and urine (eg, blood, bilirubin, WBC, RBC, protein) ([Table 12-1](#)) will be conducted to provide additional clinical data. In addition, to assess potential impact on the central nervous system, physical examination, including neurological examination and suicidal risk monitoring by Columbia Suicide Severity Rating Scale (C-SSRS) will be implemented throughout the double-blind and safety follow-up period. To assess potential impact on the respiratory and cardiovascular system, vital signs including systolic/diastolic blood pressure, heart rate, respiratory rate, and body temperature will be assessed during every visit when the investigational product is administered and electrocardiograms will be assessed on day 1, week 8, week 12, week 20, and week 28. Energy metabolism will be assessed through repeated HbA1C and fasting glucose tests as well as body weight monitoring. Homeostatic control is closely monitored through vital sign assessment (eg, body temperature) and various lab tests (eg, blood sodium, potassium, calcium and glucose levels; urine pH and glucose level). Furthermore,

appropriate inclusion/exclusion criteria and precautionary measures have been implemented within the study protocol to ensure subject safety remains paramount.

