#### **9.2.3.3      Electrocardiograms (ECGs)**

Subject must be in supine position in a rested and calm state for at least 5 minutes before ECG assessment is conducted. If the subject is unable to be in the supine position, the subject should be in most recumbent position as possible. The ECG must include the following measurements: Heart Rate, QRS, QT, QTc, and PR intervals.

Study centers will use ECG equipment supplied by the central vendor. It is the responsibility of the investigator to determine if the ECG tracings are consistent with a

subject's safe participation in the study. The investigator will review all ECGs. Once signed, the original ECG tracing will be retained with the subject's source documents. The central reader will review all ECGs. At the request of the sponsor, a copy of the original ECG will be made available to Amgen.

Any ECG abnormality noted by the central reader must be evaluated by the investigator and discussed with the Amgen Medical Monitor as deemed necessary to determine if the ECG finding is representative of an unstable or clinically significant medical condition.

Refer to the central ECG reader manual for details.

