5.3 Study Points of Reference

Baseline Period

The 4-week baseline period starts when the subject has met all Part 1 eligibility criteria (refer to Section 6.1 of the protocol) and is entered in the baseline period (refer to Section 6.6 of the protocol) and ends when the subject is considered a screen failure (discontinuation before randomization and/or subject does not meet all baseline eligibility criteria, refer to [Section 6.3](#)) or randomized.

The first day of the baseline period is the day that the subject records the first assessment in the eDiary and the last day of this period is the date the subject records the last assessment prior to the first dose of IP on Study Day 1.

The baseline assessment is defined as the last non-missing measurement for the endpoint of interest taken before the first dose of IP. In cases where baseline measurements are taken on the same day as the first dose of IP, it will be assumed that these measurements are taken prior to IP being administered. For subjects who are randomized but not dosed after the randomization, the baseline of the study is defined as the last non-missing measurement prior to or on the date of randomization. Above definition applies to safety measurements and PROs collected at office **visits** (HIT-6, CAPS and MMIDAS).

For measurements with multiple individual items such as C-SSRS and ECG, all individual items from the same set of measurement will be used for analysis. If some items from the same set are missing, then the latest complete set of measurement prior to the first dose of IP will be used as baseline. A similar rule holds for post-baseline measurements.

Baseline assessment of data collected from eDiary will be summarized as monthly measurements using data collected during baseline period.

Study Day 1

Study Day 1 is defined as the first IP dose date. For subjects who are randomized but not dosed after randomization, the Study Day 1 is defined as the date of randomization.

Study Day

Study Day is defined as the number of days from Study Day 1.

Before Study Day 1:

Study Day = (date of interest – date of Study Day 1)

On or after Study Day 1:

Study Day = (date of interest – date of Study Day 1) + 1

Therefore the day prior to Study Day 1 is -1.

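### ECGs are a stated cardiovascular safety check with central review of every tracing, yet no by-arm summary of PR, QRS, QTc outliers or new abnormal reads is planned

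*SAP*

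**What the plan says.** Protocol 3.3 describes the safety monitoring by body system. Its cardiovascular sentence begins "To assess potential impact on the respiratory and cardiovascular system, vital signs including systolic/diastolic blood pressure" and ends by saying that "electrocardiograms will be assessed on day 1, week 8, week 12, week 20, and week 28". ECGs and vital signs are thus named together for one purpose.

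Protocol 9.2.3.3 sets out how the tracings are taken:
- Equipment: "Study centers will use ECG equipment supplied by the central vendor".
- Conditions: "Subject must be in supine position in a rested and calm state for at least 5 minutes before ECG assessment is conducted". The most recumbent position possible is the fallback.
- Content: "The ECG must include the following measurements: Heart Rate, QRS, QT, QTc, and PR intervals".
- Review: "The central reader will review all ECGs". The investigator also reviews every tracing and must evaluate any abnormality that the central reader notes.

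SAP 9.6.8 and Protocol 10.4.3.3.6 carry the same text. Both describe the ECGs as standard-of-care recordings for routine monitoring, say they may fall short of what QTc evaluation demands, and conclude that "summaries and statistical analyses of ECG measurements are not planned". SAP 13 places ECG data among the data the plan does not cover.

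SAP 5.3, in its baseline rule, still says: "For measurements with multiple individual items such as C-SSRS and ECG, all individual items from the same set of measurement will be used for analysis".

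**The concern.** The protocol tells ethics committees and investigators that ECGs help to assess cardiovascular impact, and it specifies a uniform way of recording and reviewing them. The analysis sections then leave the results out of every planned table. The reason given concerns QTc alone, while the decision covers every ECG measurement.

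What is at stake is a pattern visible only in aggregate: a modest shift in PR or QRS in one arm, or several outliers or new abnormal reads in one arm that no single investigator thought worth reporting. Protocol 3.3 describes the target peptide as vasoactive with cardiovascular functions, and the randomized placebo arm is the natural comparison for such a pattern. With no planned table, that comparison would not be reported.

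**Working it through.** There is no figure in the plan to reproduce. The check is mainly a comparison of the texts, followed by a count and an illustration of feasibility.

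**1. Purpose against decision.** Protocol 3.3 gives ECGs a cardiovascular safety purpose. Protocol 10.4.3.3.6, SAP 9.6.8 and SAP 13 plan no output that serves it. The conflict lies partly inside the protocol; the SAP follows the protocol's own statistics section.

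**2. Procedure against reason.** The reason has two parts.
- *Standard-of-care conduct.* This fits poorly with Protocol 9.2.3.3, where equipment comes from one vendor, the intervals are fixed and every tracing is centrally reviewed.
- *Possibly too little rigor for QTc.* Protocol 9.2.3.3 does not refute this. It specifies no replicate recordings, no QT correction formula and no timing relative to dose.

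**3. What the QTc reason covers.** Item by item:
- PR and QRS: not QTc measurements, so no reason is given.
- New abnormal central reads: a categorical finding on any feature of the tracing, so no reason is given.
- QTc change and QTc outliers: the caveat limits what may be concluded. It can be printed with the table and does not require that the table be absent.
- Heart rate: already covered. SAP 9.6.4 plans change from baseline by arm over time and counts of pulse below 60 or above 100 bpm, and SAP Table 5-5 gives vital-sign windows from day 1 to week 28.

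**4. Other routes to a table.** Under Protocol Appendix 4, an ECG abnormality becomes an adverse event if the investigator considers it clinically significant; adverse events are tabulated by arm. Findings below that threshold have no route. The Data Review Team (Protocol 10.4.2, SAP 7.1) sees group-level summaries, but neither document says that they include ECGs.

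**5. Amount of data.** Inputs: about 335 subjects allocated 4:3:3 (Protocol 5.1), giving 335 x 0.4 = 134 on placebo and 335 x 0.3 = 100.5 on each dose; ECGs at day 1 and four later visits (Protocol 3.3). After day 1 there are at most 335 x 4 = 1,340 tracings, that is 134 x 4 = 536 on placebo and 100.5 x 4 = 402 on each dose. This assumes no dropout and no missed visit.

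**6. Would a table be informative?** This is an illustration only, as the documents give no SD and no outlier rate.
- 95% half-width for a QTc change, one dose against placebo = 1.96 x SD x sqrt(1/134 + 1/100) = 1.96 x SD x 0.132. For assumed SDs of 10, 15, 20 and 25 ms this gives 2.6, 3.9, 5.2 and 6.5 ms.
- Chance of at least one outlier among 100 subjects = 1 - (1 - p)^100. For assumed true rates of 1% and 3% this gives 63% and 95%.

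Descriptive tables are therefore feasible, and some outliers should be expected in each arm even if the drug has no effect.

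**The case against.** The strongest case for leaving the plan alone has five parts.

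- **The plan is consistent on the decision.** Protocol and SAP carry the same ECG text, and ECG is not among the safety endpoints in the visible text. This stands, and it means that a change to the SAP alone would create a mismatch.
- **The ECGs serve individual monitoring.** The investigator judges each tracing, must evaluate whatever the central reader notes, and reports significant findings as adverse events, which are tabulated by arm. This is a real safeguard for the individual subject. It does not show a group pattern made of findings below the reporting threshold.
- **The reason given is narrower than it looks.** A reader might infer that the plan prohibits ECG summaries, or that it calls the tracings unstandardized and is contradicted by its own procedure. The text supports neither: summaries are simply not planned, and the stated worry is rigor for QTc, which Protocol 9.2.3.3 leaves open. Only the standard-of-care label conflicts with that section.
- **The SAP 5.3 wording proves little.** A reader might take it as evidence that an ECG analysis was intended. It is a general rule for multi-item measurements, and SAP 5.4 has no ECG visit windows, so a drafting leftover is the more likely explanation.
- **Prior concern is low and the cost is unverified.** Protocol 3.3 reports no drug-related ECG changes in 26 weeks of monkey dosing. The documents say that the central reader reviews tracings, but not that centrally measured intervals enter the analysis database. Both points stand; the second must be settled before the tables are promised.

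**Conclusion.** The point holds as a gap in planned safety reporting. PR, QRS, QTc outliers and new abnormal central reads have no by-arm table, although the protocol assigns ECGs a cardiovascular safety purpose and sets a uniform procedure with central review. The QTc caveat may be right on its own terms, but it does not justify omitting the rest.

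The size is modest: at most about 1,340 post-day-1 tracings, with no bearing on the efficacy inference. A reader might infer that a heart-rate shift would go unseen or that the randomized safety comparison is lost altogether. The documents do not support that, because heart rate and blood pressure are summarized by arm under SAP 9.6.4. This is a cheap improvement that should be made, not a defect that undermines the trial.

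The conclusion assumes that interval measurements and abnormality flags from the central reader are, or can be, transferred in usable form, and that the Data Review Team's summaries, whose content is not described, do not already fill the gap in reporting.

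**What to change.** Change Protocol 10.4.3.3.6 and SAP 9.6.8 together, so that both plan:
- descriptive summaries by arm and visit of change from baseline in PR, QRS and QTc;
- counts of subjects by arm with post-baseline QTc outliers and with new abnormal central reads;
- no testing, with a statement that this is safety monitoring and not a QT assessment.

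Remove ECG from SAP 13 and drop the standard-of-care description, or reconcile it with Protocol 9.2.3.3. Add ECG visit windows to SAP 5.4. State which tracing serves as baseline under SAP 5.3, since ECG timing relative to dose is not given. Fix the outlier categories and the QT correction formula before unblinding. Heart rate needs no new table.

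If the sponsor prefers no summary, Protocol 3.3 should explain how ECGs serve their stated purpose without one, and the ECG mention in SAP 5.3 should go.

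The cost is a few tables, one visit-window table and a protocol text change, with no new procedure for subjects. Some chance outliers will need comment. The sponsor must first confirm that central-reader measurements reach the analysis database; if they do not, a data transfer is an added cost.

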9.6.9 Antibody Formation

The number and percentage of subjects who develop anti-AMG 301 antibodies (binding) will be tabulated by treatment group for entire study. The list of subjects with positive binding antibody at any time will be provided.

9.6.10 Exposure to Investigational Product

The total dose of investigational product and the proportion of subjects receiving each dose level will be summarized using descriptive statistics. Descriptive statistics will be produced to describe the exposure to investigational product by treatment group. The number and percentage of subjects with dose change, reason for dose change and duration of exposure to IP in days will be summarized by treatment group.

9.6.11 Exposure to Concomitant Medication

Number and proportion of subjects receiving acute headache-related will be summarized by acute medication category for each treatment group.

9.6.12 Exposure to Prior Prophylactic Medication

Number and percentage of subjects receiving prior prophylactic medication by categories and discontinuation reasons will be summarized by treatment group.

9.6.13 Cardiovascular Medical History

Number and proportion of subjects reporting cardiovascular medical history will be summarized by treatment group.

9.6.14 Cardiac and Diabetes Risk Factors

Number and proportion of subjects reporting cardiac and diabetes risk factors will be summarized by treatment group.

[figure not shown]
9.7 Other Analyses

9.7.1 Analyses of Pharmacokinetic or Pharmacokinetic/Pharmacodynamic Endpoints

The pharmacokinetic analysis will be carried out for all subjects who received any AMG 301 doses for estimation of exposure parameters. The exposure parameters will be summarized by dose level and treatment time with descriptive statistics. Actual dose and actual sampling time will be used in the analysis. Dosing interruptions, sampling errors

or administration errors which may impact on the assessment will be taken into account in the analysis. Individual concentration-time data will be provided as a listing.

CCI

PK analyses will be done by Clinical Pharmacology Modeling and Simulation (CPMS).

All PK-related tables, figures, listings and other deliverables will be generated by Clinical Pharmacology Modeling and Simulation (CPMS).

9.7.2 Analyses of Clinical Outcome Assessments

See Section 9.5.4.

10. Changes From Protocol-specified Analyses

The endpoint of change from the baseline period in monthly days with impact on everyday activities as measured by the MPFID domain at assessment time points was not included in the protocol but was added to the SAP to assess the effect of AMG 301 compared to placebo on change from the baseline period in monthly days with impact on everyday activities as measured by the MPFID domain.

The protocol stated that for secondary endpoints comparison between treatment groups for categorical data will be performed using generalized linear mixed effects model on observed data adjusting for baseline values and stratification factors with appropriate contrasts for pairwise comparisons as well as CMH test. The analysis method will be changed so that comparison between treatment groups for secondary endpoints will be performed using only CMH tests on observed data with stratification factors for categorical data.

The protocol stated that the FAS consists of all subjects who were enrolled in the study. This definition will be changed so that the FAS consists of all subjects who were randomized in the study.

Three subgroups were added: prior use of anti-CGRP medication, CAPS score at baseline, and response status to AMG 334.

11. Literature Citations / References

AMG 301 Investigator Brochure. Thousand Oaks, CA. Amgen Inc.

Amgen. A Phase 2, Randomized, Double-blind, Placebo-controlled Study to Evaluate the Efficacy and Safety of AMG 334 in Chronic Migraine Prevention. AMG 334 Study 20120295. 23 July 2015.

Amgen. A Phase 3, Randomized, Double-blind, Placebo-controlled Study to Evaluate the Efficacy and Safety of AMG 334 in Migraine Prevention. AMG 334 Study 20120296. 24 March 2015.

Edvinsson L. Role of VIP/PACAP in primary headaches. *Cephalgia* 2013;33:1070-1072.

- **Efficacy data during Safety Follow up period, with the exception of change from baseline in monthly headache days from week 12 to week 16.**
- General comments
- Data from pharmacogenetics substudy.

14. Appendices

**Appendix A. Technical Detail and Information Regarding Statistical Procedures
and Programming**

N/A

Appendix B. Code Fragment

[figure not shown]
CCI

CCI

[figure not shown]
CCI

[figure not shown]
CCI

CCI

CCI

Appendix C. Reference Values/Toxicity Grades

[figure not shown]
Adverse event severity and laboratory toxicity are graded based on NCI Common Toxicity Criteria version 4 or higher, which is available at the following:
http://evs.nci.nih.gov/ftp1/CTCAE/CTCAE_4.03_2010-06-14_QuickReference_5x7.pdf

Appendix D. Concomitant Medications

[figure not shown]
N/A

Appendix E. Clinical Outcome Assessment Forms/Instruments

CCI

[figure not shown]
CCI

[figure not shown]
CCI

CCI

[figure not shown]
CCI

CCI

CCI

CCI

Appendix F. Health Economic Forms/Instruments

N/A

Appendix G. Details of PK or PK/PD Methods for Modeling

N/A
